PROTOCOL SYNOPSIS

TITLE	A Double-Blind, Randomized, Crossover Design Study To Compare The Rocuronium Reversal By Sugammadex To Succinylcholine For Electroconvulsive Therapy (ECT)
SPONSOR	[name]
FUNDING ORGANIZATION	Merck & Co, Inc.
NUMBER OF SITES	1
RATIONALE	
The purpose of this study is to find out if a novel drug, sugammadex, can be used to reverse the muscle relaxation during the Electroconvulsive Therapy (ECT). ECT exerts its therapeutic effect by inducing generalized seizures. To protect the patients from harmful seizure injury, neuromuscular blockade is used to control excessive muscle movement during the treatment. Since the optimal length of therapeutic seizure effects is brief, fast recovery of the neuromuscular function after the treatment is desirable.
 
Succinylcholine has been traditionally used in ECT for muscle relaxation because of its fast recovery after the procedure, but with obvious limitations and side-effects. Rocuronium is a different muscle relaxant providing excellent blocking conditions and has been commonly used in surgery, but not in ECT because of its long duration of action. Sugammadex is a novel reversal drug for rocuronium, which has recently been approved by the FDA. Sugammadex can reverse the action of rocuronium on neuromuscular blockade. Researchers want to learn whether sugammadex can be used in combination with rocuronium to provide a timely recovery of neuromuscular function after the ECT treatment.

STUDY DESIGN	This is a randomized, double-blind, placebo-controlled phase 2 study.
PRIMARY OBJECTIVE	The primary objective is to further explore the pharmacology of sugammadex in electroconvulsive therapy (ECT) by measuring neuromuscular recovery time from sugammadex reversal of rocuronium, compared to traditionally used succinylcholine.
SECONDARY OBJECTIVES	Secondary aims are to document the safety and tolerability (adverse event rates) of rocuronium/sugammadex compared to succinylcholine in ECT patients, and to explore perioperative efficacy and efficiency of sugammadex reversal of rocuronium in ECT procedures.

NUMBER OF SUBJECTS	50
SUBJECT SELECTION CRITERIA	
Inclusion Criteria:
 
 • Age \geq 18 years • Eligible and scheduled for ECT • Has the capacity to consent for the study 
Exclusion Criteria:
 
 • Any acute major organ failure in the last 30 days • Any known or suspected neuromuscular disorders • Any history of allergic reaction or intolerance to sugammadex, rocuronium, or succinylcholine • Any conditions with severe renal impairment, including those requiring dialysis • Anyone currently taking hormonal contraceptives • Anyone taking anti-coagulants, including vitamin K antagonists, unfractionated heparin, low molecular weight heparinoids, rivaroxaban, and dabigatran
TEST PRODUCT, DOSE, AND ROUTE OF ADMINISTRATION	Sugammadex at 4 mg/kg, IV (after rocuronium is administered for ECT)
CONTROL PRODUCT, DOSE AND ROUTE OF ADMINISTRATION	Succinylcholine at 1 mg/kg IV + normal saline IV
DURATION OF SUBJECT PARTICIPATION AND DURATION OF STUDY	
Subjects will be on study for up to two treatments
 
Screening: up to 7 days
 
Treatment: standard procedure time (about 2 hours)
 
Follow-up: 24 hours by phone
 
The total duration of the study is expected to be one month for subject recruitment and for final subject follow-up.

CONCOMITANT MEDICATIONS	
Allowed:
 
Standard therapy for patients' medical diseases is allowed except for treatments noted in the exclusion criteria described above and as noted in the prohibited medications section below.
 
Prohibited:
 
• hormonal contraceptives• anti-coagulants, including vitamin K antagonists, unfractionated heparin, low molecular weight heparinoids, rivaroxaban, and dabigatran
EFFICACY EVALUATIONS	
PRIMARY ENDPOINT	
• Neuromuscular recovery time from sugammadex reversal of rocuronium, compared to traditionally used succinylcholine.
SECONDARY ENDPOINTS	
• Explore perioperative efficacy and efficiency of sugammadex reversal of rocuronium in ECT procedures.
OTHER EVALUATIONS	
SAFETY EVALUATIONS	
• Safety and tolerability (adverse event rates)
PLANNED INTERIM ANALYSES	An interim analysis is planned after approximately 30% of the patients have been enrolled and completed follow-up to assess safety and provide estimates of within and between patient variability in the recovery time of muscle relaxants. The interim analysis for safety will be conducted by the study team. Serious adverse events will be monitored by the investigators on an ongoing basis throughout the study.
STATISTICS Primary Analysis Plan	This is a two-period, two-treatment, 2x2 cross-over study. Although it is highly likely that the washout period is adequate for eliminating the first order carry-over effects since all repeated procedures are scheduled at least 48 hours apart, which exceeds the duration for all the involved medications, we will exam the period and carryover effects using a term for time period and an interaction term between the treatment group and time period. Intent-to treat analyses will be used for primary and secondary outcomes. For the primary outcome, the comparison of recovery time of T1 to 90% baseline, a continuous variable, between the groups of rocuronium /sugammadex and the

	succinylcholine /saline placebo, will be analyzed using the two sample t test.
Rationale for Number of Subjects	
Based on the study by Lee, et al,⁸ comparing high dosage of rocuronium 1.2 mg/kg in combination with high dosage reversal of sugammadex 16mg/kg with succinylcholine 1mg/kg, the recovery time T1 to 90% in succinylcholine was 10.9 ± 2.4 minutes. The reported T1 to 90% 4mg/kg sugammadex reversed recovery counted from time of rocuronium 0.6 mg/kg (the same proposed dosage as in our study) administration ranged from 6 to 9.3 minutes.^{5, 10} With our estimation of two-tailed $\alpha=0.05$, $\beta=0.2$, the reported minimum mean difference of 1.6 (10.9 minus 9.3) minutes, SD of succinylcholine of 2.4 minutes, the calculated sample size for a cross-over trial would be 35.
 
At UCSF, there are usually 60 ECT patients each year. With a conservative estimate of 75% consent rate, we will have at least 45 patients to participate in the study. Even conservatively allowing a 20% drop-off rate, we feel that our enrollment up to 50 will provide sufficient power for the study.

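### Does a stated one-month study duration matter when the expected 45 participants are a full year's intake?

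*Combined protocol and SAP*

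**What the plan says.** The synopsis entry on duration of subject participation and duration of study lists the time each subject spends: up to two treatments, screening of up to 7 days, procedures of about 2 hours and a phone call at 24 hours. It then closes with a sentence on the study as a whole: "The total duration of the study is expected to be one month for subject recruitment and for final subject follow-up".

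The Rationale for Number of Subjects describes the supply of patients. At the centre "there are usually 60 ECT patients each year", and "With a conservative estimate of 75% consent rate" leads to the statement that "we will have at least 45 patients to participate in the study". The same entry says that "the calculated sample size for a cross-over trial would be 35", allows for 20% drop-off, and concludes that "our enrollment up to 50 will provide sufficient power for the study". Elsewhere the synopsis gives one site and 50 subjects. The text supplied states no other recruitment period.

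**The concern.** The two entries describe recruitment on very different time scales. The 45 participants are an annual figure, yet the duration sentence fits recruitment and the last follow-up into a single month. Read literally and with even accrual, a one-month window would yield about 4 subjects, far below the 35 that the power calculation calls for. If recruitment really stopped then, the trial could not answer its primary question. A timeline that is too short by about a factor of ten could also mislead those who plan staffing, funding and oversight.

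**Working it through.** Inputs, all from the synopsis: 60 ECT patients a year, 75% consent, at least 45 participants, 20% drop-off, calculated size 35, enrolment up to 50 (Rationale for Number of Subjects); 50 subjects and one site (the entries so named); one month in total (duration entry). Losses to the exclusion criteria are not deducted because no rate is given; they could only lengthen the times below.

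*The plan's own figure.* 60 × 0.75 = 45. This reproduces the stated number and shows that it is a twelve-month count.

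*Even accrual (assumed).* 60 / 12 = 5 patients a month, and 5 × 0.75 = 3.75 consenting. Months needed = target / monthly rate. The target of 44 is the enrolment that leaves 35 completers: 35 / 0.8 = 43.75.

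| Target | Months at 75% consent (3.75 a month) | Months at 100% consent (5 a month) |
|---|---|---|
| 35 | 9.3 | 7.0 |
| 44 | 11.7 | 8.8 |
| 45 | 12.0 | 9.0 |
| 50 | 13.3 | 10.0 |

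One month gives 3.75 subjects: 3.75 / 35 = 10.7%, 3.75 / 45 = 8.3% and 3.75 / 50 = 7.5% of the respective targets.

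*Uneven accrual.* Patients who must be available in the one month = target / 0.75:

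- 35 subjects: 46.7, so 47 of the year's 60 (78%)
- 44 subjects: 58.7, so 59 of 60
- 45 subjects: 60 of 60
- 50 subjects: 66.7, so 67, more than the year's supply

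One month is therefore very unlikely for 35 to 45. It is strictly impossible only for 50, and only while consent stays below 50 / 60 = 83%.

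*What depends on the month.*

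- Sample size: the stated inputs are a difference of 1.6 minutes, an SD of 2.4 minutes, two-tailed α of 0.05 and β of 0.2. With the normal approximation and no within-patient correlation, 2 × (1.960 + 0.842)² × (2.4 / 1.6)² = 35.3, close to the stated 35. No calendar time enters.
- Power after drop-off: a year's intake gives 45 × 0.8 = 36 completers, and 50 enrolled give 50 × 0.8 = 40. Both reach 35.
- Interim analysis: it is triggered once about 30% of patients are enrolled and followed up, that is 0.30 × 50 = 15. At 3.75 a month this comes at 15 / 3.75 = 4 months. The calendar date moves; the trigger does not.
- Primary analysis: it compares recovery times between treatments and makes no use of study duration.

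**The case for a change.** The best case for acting is that this is a plain, checkable contradiction and one sentence would cure it. The month is too short by a factor of roughly seven to thirteen, whatever the target and even if every patient consents. The nominal 50 subjects cannot be reached in a month at the stated consent rate. The month would also have to hold the last subject's second procedure, a minimum of 48 hours after the first, and the follow-up call. Nor does reading the month as each subject's own time fit easily, because the sentence refers to the whole study and names recruitment.

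Most of that stands as description: the entries disagree, and nothing in the text reconciles them. The supposed consequence does not stand. Stopping at about 4 subjects requires the month to act as a closing date, whereas the sentence only gives an expectation and enrolment is defined by a number of patients. The figure of 4 also assumes five newly available patients each month. Patients already in a course of ECT could enrol at the start, and the plan gives no number for them. Finally, the rationale describes 75% as conservative and 45 as a minimum, so 3.75 a month is a low-side rate.

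**Conclusion.** The inconsistency is real but clerical. At the plan's own rates and with even accrual, recruitment would take about 9 months for 35 subjects, 12 for 45 and 13 for 50, not one month. With uneven accrual, one month is implausible for 35 to 45 and impossible for 50 at 75% consent. The error lies wholly in a stated timeline. It does not reach the sample size, the power, the interim trigger, the analysis or the conclusions, provided that recruitment runs until the target count is met, which is the natural reading of a plan that sets enrolment by number. A study team would see after the first weeks that recruitment needs most of a year or more, and would continue. Rewording the sentence would be a reasonable editorial tidy-up whenever the document is next revised, but it would change nothing in how the trial is run or interpreted, so no change to the plan is called for.

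### Does the missing time zero in the primary endpoint bias the recovery-time comparison towards sugammadex?

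*Combined protocol and SAP*

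**What the plan says.** All references are to the protocol synopsis in the combined protocol and SAP.

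- **Primary Objective:** the pharmacology is to be explored by "measuring neuromuscular recovery time from sugammadex reversal of rocuronium, compared to traditionally used succinylcholine".
- **Efficacy Evaluations, Primary Endpoint:** "Neuromuscular recovery time from sugammadex reversal of rocuronium, compared to traditionally used succinylcholine". No start time is given for either treatment.
- **Statistics, Primary Analysis Plan:** the outcome is "the comparison of recovery time of T1 to 90% baseline, a continuous variable", compared between rocuronium/sugammadex and succinylcholine/saline. This gives the end of the interval only.
- **Rationale for Number of Subjects:** for succinylcholine, "the recovery time T1 to 90% in succinylcholine was 10.9 ± 2.4 minutes", with no clock start named. For the test regimen, "sugammadex reversed recovery counted from time of rocuronium 0.6 mg/kg (the same proposed dosage as in our study) administration ranged from 6 to 9.3 minutes". The trial is sized on "the reported minimum mean difference of 1.6 (10.9 minus 9.3) minutes".
- **Test Product and Control Product:** sugammadex follows rocuronium after an interval that is not given. The control is succinylcholine plus intravenous saline.

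**The concern.** A recovery time needs a start and an end, and here the start of the primary outcome is not written down. The word *from* in the objective and endpoint can be taken as naming the start, so that the test clock runs from the sugammadex injection. Succinylcholine has no reversal agent, so its clock would seem to run from the succinylcholine injection. The wait between rocuronium and sugammadex would then count under neither treatment, although it is part of the patient's time under block in the test period.

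An error of that kind would be serious. It follows treatment rather than patient or period, so neither the crossover nor the test statistic would remove it. It would always favour sugammadex, and the planned effect is small enough for a short interval to match it. The observed difference would also no longer correspond to the one used for sizing, because the test-arm planning value is "recovery counted from time of rocuronium 0.6 mg/kg" and so includes the wait.

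**Working it through.** **Inputs.** From Rationale for Number of Subjects: succinylcholine mean 10.9 min, SD 2.4 min; least favourable test mean 9.3 min; two-sided alpha 0.05; beta 0.2; stated n = 35. Assumed, because the documents do not give it: L, the interval in minutes between the first injection (relaxant) and the second (sugammadex or saline).

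**Step 1: the plan's own figures.** Difference = 10.9 - 9.3 = 1.6 min. With the normal approximation, n = 2 × (1.960 + 0.842)² × 2.4² / 1.6² = 2 × 7.849 × 2.25 = 35.3. This agrees with the stated 35, apart from rounding up to 36.

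**Step 2: the planned difference under each clock.**

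| Clock start | Difference (min) |
|---|---|
| Both from the relaxant | 10.9 - 9.3 = 1.6 |
| Both from the second injection, same L | (10.9 - L) - (9.3 - L) = 1.6 |
| Test from sugammadex, control from succinylcholine | 10.9 - (9.3 - L) = 1.6 + L |

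The first two rows assume that the 10.9 min was also counted from the relaxant. Subtracting a constant L leaves the SD at 2.4, so n stays at 35.3 in both. Only the third row is biased, and the bias is exactly L.

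**Step 3: size of the bias in the third row.** L = 1, 2 or 3 gives 2.6, 3.6 or 4.6 min, an excess of 1/1.6 = 63%, 2/1.6 = 125% or 3/1.6 = 188% of the planned effect. Suppose the treatments are truly equal when timed from the relaxant, with 35 values each. Then SE = 2.4 × √(2/35) = 0.574, and the chance of a significant result favouring sugammadex is Φ(L/0.574 - 1.96):

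| L (min) | Chance |
|---|---|
| 1 | 41% |
| 1.6 | 80% |
| 2 | 94% |
| 3 | over 99% |

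The nominal rate in that direction is 2.5%. The danger would be real if the third row were the plan.

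**Step 4: is the third row the plan?** Four places in the synopsis bear on this.

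- The title, the secondary objective and the secondary endpoint use the idea of sugammadex reversing rocuronium as the name of the test regimen, with no clock implied. The primary endpoint reads naturally in the same way: recovery time under one regimen against recovery time under the other.
- The only clock start stated anywhere is rocuronium administration, at what the rationale says is this study's rocuronium dose.
- The Planned Interim Analyses row attaches recovery time to the muscle relaxants, not to the reversal agent.
- Title and Study Design describe a double-blind, placebo-controlled trial, and the control includes saline. Each period therefore has a first and a second injection. An assessor who does not know the treatment cannot start the clock at the second injection for one drug and at the first for the other.

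Nothing in the synopsis calls for the third row. The evidence favours the first, and the second leaves the planned difference unchanged when the intervals are equal.

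**The case for a change.** The best case for a change is that a primary endpoint should not depend on how a preposition is read. Even if *from* means *resulting from*, the start is still undefined. The sample-size text describes published planning data and is not a measurement rule for this trial. The start behind the 10.9 minutes is not stated at all. Blinding limits the assessor, but an analyst working after unblinding could still compute the intervals differently by treatment. Writing down one time zero would cost a line.

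Much of this stands. The definition is missing, the planning text does not formally supply it, and the match with the planning basis is documented for the test regimen only. If the interval between injections differed by treatment, timing both from the second injection would move the difference by the gap between the two intervals. What does not stand is the step from an unstated start to a built-in advantage. That step needs different clocks for the two treatments, which no sentence prescribes and which sit badly with a blinded, saline-controlled comparison of a single variable. It also needs a value for L that the documents do not contain. The percentages in Step 3 describe that hypothetical case and do not measure a fault in the plan.

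**Conclusion.** No change to the plan is needed. The endpoint lacks an explicit time zero, but an analyst working from the planning basis would time both treatments from the relaxant, and the planned difference of 1.6 minutes and the sample size of 35 would stay as they are. Timing both from the second injection at an equal interval gives the same 1.6 minutes. A bias equal to the rocuronium-to-sugammadex interval (63% of the planned effect per minute) arises only if the two treatments are timed from different events, which the plan does not require.

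This rests on three assumptions: the blind holds for whoever records the times, the 10.9 minutes was counted from succinylcholine, and, for the second-injection clock only, the interval between injections is the same under both treatments. The text available is a synopsis, where operational detail of this kind is often brief, so its absence is weak evidence of a design error.

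### Does the interim look at recovery-time variability force the study team to break the blind or accept a biased estimate?

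*Combined protocol and SAP*

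**What the plan says.** The Study Design row of the synopsis states: "This is a randomized, double-blind, placebo-controlled phase 2 study". The Primary Analysis Plan adds: "This is a two-period, two-treatment, 2x2 cross-over study". Its primary outcome is "the comparison of recovery time of T1 to 90% baseline, a continuous variable".

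The Planned Interim Analyses row sets one look: "An interim analysis is planned after approximately 30% of the patients have been enrolled and completed follow-up". The look has two purposes. One is safety. The other is to "provide estimates of within and between patient variability in the recovery time of muscle relaxants". On who does the work there is one sentence: "The interim analysis for safety will be conducted by the study team". The row then leaves continuing surveillance of serious adverse events to the investigators.

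The supplied text does not say who produces the variability estimates, whether the data are pooled, coded or by treatment, or what the estimates are for. It names no interim efficacy comparison, stopping rule or sample-size revision.

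**The concern.** Within-patient variance is a parameter of the primary outcome, and in a crossover each patient's two results differ partly because the treatments differ. That part has to be removed before the remainder can be called within-patient variability. The obvious way is to use the treatment labels. If the people running a double-blind, single-site trial use them, they learn the trend after 15 patients and then treat and assess the other 35. If they do not, the usual estimate is too large.

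The sample size makes the variance look important. It rests on an SD of 2.4 minutes taken from a cited study's succinylcholine results, and the plan does not say whether that is a within-patient figure. A look that could test this assumption has neither a method nor a use attached to it.

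**Working it through.** **Inputs.** From Rationale for Number of Subjects: "the reported minimum mean difference of 1.6 (10.9 minus 9.3) minutes", SD 2.4 minutes, two-sided α 0.05, power 80%, calculated size 35, enrolment up to 50, and a reported test-arm recovery range of 6 to 9.3 minutes. From Planned Interim Analyses: about 30%. Two inputs are assumptions because the plan gives neither: 1:1 allocation to sequences, and a within-patient correlation ρ of 0, 0.5 or 0.7.

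**The plan's own figure.** Total N = 2 × 2.4² × (1.960 + 0.842)² / 1.6² = 35.3, which agrees with the stated 35 (36 if rounded up). So 2.4 has been used as if it were the within-patient SD, which corresponds to ρ = 0.

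**Timing.** 0.30 × 50 = 15 patients at the look, leaving 35.

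**Bias when labels are ignored.** Each patient's period difference is a period effect, plus or minus the treatment effect δ (the sign depends on sequence), plus error with variance 2σ_w². With equal sequences its variance is 2σ_w² + δ². Halved, this gives σ_w² + δ²/2. With σ_w² = 5.76 × (1 − ρ) and δ = 1.6, the excess is 1.28 min²:

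| ρ | true σ_w² | label-free | variance | SD |
|---|---|---|---|---|
| 0 | 5.76 | 7.04 | +22% | +11% |
| 0.5 | 2.88 | 4.16 | +44% | +20% |
| 0.7 | 1.73 | 3.01 | +74% | +32% |

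At the far end of the plan's range, δ = 10.9 − 6 = 4.9, the excess is 4.9²/2 = 12.0 min² and the SD is overstated by 76%, 127% or 182%.

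**Is unblinding needed to avoid this?** Simulation of 15 patients (8 and 7 per sequence, ρ = 0, δ = 1.6, 200,000 runs) gave these mean estimates against a true 5.76:

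- Labels ignored: 7.13. This is slightly above 7.04 because the sample variance with an 8/7 split multiplies 1.28 by 4 × 8 × 7/(15 × 14) = 1.067.
- Variance taken within each sequence and pooled: 5.75. This needs only to know which patients share a sequence, so codes without treatment names are enough.
- Sums over complete balanced blocks, with no labels at all (assumed block size 4, 16 patients): 5.76. It is less precise, with a standard deviation of the estimate of 4.70 against 2.26 for the within-sequence method.

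Two routes therefore give an unbiased variance without treatment identity. The pooled estimate errs towards a larger variance.

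**What the estimate could support.** With 13 degrees of freedom, the 95% limits for the SD are 0.725 and 1.611 times the estimate. Required N scales with the square: 35 × 0.725² ≈ 18 and 35 × 1.611² ≈ 91. Even an unbiased estimate from 15 patients could not confirm a requirement of 35.

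**The case for a change.** The strongest case for a change is that the safety objective is comparative, so a safety analysis by the study team can naturally be read as one by treatment, and nothing rules that out. At a single site the same people may go on to treat up to 35 more patients and collect adverse events by telephone, where knowing a trend could colour the record. The variance bias at δ = 4.9 is large. A few sentences would settle the matter: the holder of the randomisation list releases only SDs, the team sees adverse events pooled, and the estimate is used to confirm the number of completers within 50.

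Part of this stands. The plan is silent on the points listed, and a pooled estimate could be badly inflated if the true difference is large. But a risk inferred from silence is not a planned unblinding. The supplied text is a synopsis with no section on randomisation or blinding procedures, so the absence of a safeguard there is weak evidence that none exists. A trend over 15 patients does not disclose the next patient's sequence.

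The suggested wording also gains little. Showing only pooled adverse events at the sole scheduled safety look gives up by-treatment safety information, which is a trade-off rather than a clear improvement. Confirming completers with limits of about 18 to 91, under a cap of 50, decides almost nothing. The plan does not say who holds the randomisation list, so the promised separation at no extra cost is itself an assumption.

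**Conclusion.** No change follows. The label-free bias is real for the usual estimator: 1.28 min² at δ = 1.6, or 11% to 32% on the SD scale, assuming 1:1 sequences and correlations of 0 to 0.7. Those SD errors lie inside the sampling limits of 0.725 to 1.611 at 15 patients. At δ = 4.9 they would exceed them, but the conclusion does not depend on the bias being small. It rests on three facts: the study team is assigned only the safety part, an unbiased variance does not require treatment identity, and no stated decision uses the estimate. With no interim efficacy test or sample-size change in the plan, there is no type I error inflation to correct.

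What remains is missing operational detail. A team working from blinded or coded data would follow the text as written and reach sound conclusions. The judgement would differ if the variability estimate were used to resize the trial, or if results by treatment went to those treating or assessing patients. The plan states neither.

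### The primary analysis applies an independent two-sample t test to paired crossover data, so its standard error, p value and confidence interval do not fit the design

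*Combined protocol and SAP*

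**What the plan says.** Under STATISTICS, Primary Analysis Plan, the synopsis states: "This is a two-period, two-treatment, 2x2 cross-over study". The section on duration of participation adds: "Subjects will be on study for up to two treatments". A patient who completes the study therefore has one recovery time under each regimen.

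The primary comparison of time to T1 90% of baseline is then set "between the groups of rocuronium /sugammadex and the" control regimen, where the text continues: "succinylcholine /saline placebo, will be analyzed using the two sample t test". The groups named are the two treatments, and the variable named is the recovery time itself.

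The same section also says: "we will exam the period and carryover effects using a term for time period and an interaction term between the treatment group and time period". Those terms are given for checking period and carryover. They are not tied to the primary comparison, and no patient effect, paired test or within-patient difference is named with them. Under PLANNED INTERIM ANALYSES, the interim look is meant to "provide estimates of within and between patient variability in the recovery time of muscle relaxants", so the plan recognises that the data have both components of variation.

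**The concern.** A two-sample t test assumes two separate sets of patients. Here the same patients supply both samples. Differences between patients, which cancel when each patient is compared with himself or herself, stay in the error term. The degrees of freedom are also wrong: 2n-2 instead of n-2 for a 2x2 crossover.

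The result is a standard error, p value and 95% interval that are correct only if a patient's two recovery times are uncorrelated. With positive correlation the interval is too wide, and a real difference can be missed because of the wrong error term alone.

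Period is also absent from the primary comparison. If completion differs by sequence, a period effect would enter the treatment estimate.

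**Working it through.** **Inputs.** From Rationale for Number of Subjects: mean difference 1.6 minutes (10.9 minus 9.3), SD 2.4 minutes (succinylcholine, from a cited study), two-sided alpha 0.05, power 0.80, stated sample size 35, drop-off 20%. The within-patient correlation rho is not given. I assume 0, 0.3, 0.5 and 0.7. No SD is given for rocuronium/sugammadex, so I assume equal SDs except where noted.

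**Step 1: the plan's own figure.** n = 2 x [SD x (1.960 + 0.842) / difference]^2 = 2 x (2.4 x 2.802 / 1.6)^2 = 35.3. Rounded up this is 36, so the stated 35 reproduces to within rounding. The formula has two readings:

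- Reading A: 2.4 is the total SD of one treatment. The result is then the size *per group* for two independent groups, which matches a crossover only at rho = 0.
- Reading B: 2.4 is the within-patient SD. The result is then the total size of a 2x2 crossover.

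The plan does not say which applies.

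**Step 2: standard errors, reading A, n = 36.**

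- Stated test: SE = 2.4 x sqrt(2/36) = 0.566 minutes, whatever rho is.
- Within-patient analysis: SE = 2.4 x sqrt(2(1-rho)/36).
- Ratio: 1/sqrt(1-rho).

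**Step 3: simulated operating characteristics, reading A** (n = 36, no period effect; a paired t test stands for the within-patient analysis).

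| rho | Correct SE (min) | SE ratio | True level of stated test | Power, stated test | Power, paired |
|---|---|---|---|---|---|
| 0 | 0.566 | 1.00 | 4.9% | 79-80% | 78-79% |
| 0.3 | 0.473 | 1.20 | 2.0% | 84% | 91% |
| 0.5 | 0.400 | 1.41 | 0.7% | 88% | 97% |
| 0.7 | 0.310 | 1.83 | 0.1% | 92-93% | over 99% |

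In terms of patients, the within-patient analysis needs 35.3 x (1-rho) for 80% power: 25, 18 and 11 at rho 0.3, 0.5 and 0.7 (normal approximation).

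**Step 4: reading B, n = 36.** The total SD is now 2.4/sqrt(1-rho): 2.87, 3.39 and 4.38 minutes at rho 0.3, 0.5 and 0.7. The stated test's SE becomes 0.676, 0.800 and 1.033 minutes, while the within-patient SE stays at 0.566. Simulated power of the stated test is 67%, 51% and 23%, against about 79% for the paired test.

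**Step 5: sensitivity.**

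- With 40 completers (50 less 20%), reading A, the stated test has about 88%, 92% and 96% power at rho 0.3, 0.5 and 0.7.
- With unequal SDs, for illustration 2.4 and 1.2 at rho 0.5, the SE ratio is sqrt(7.20/4.32) = 1.29 instead of 1.41.
- At rho = -0.2 (n = 35) the error reverses, and the true level is about 7%.

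**The case against.** The strongest reply is that the error is conservative. With positive correlation the true level is below 5%, the interval over-covers, and a significant result can be believed. Under reading A the stated test also stays above the plan's 80% power target, so the loss is measured against a better analysis and not against what was promised. The trial is an exploratory phase 2 study, rho may be small for two different agents, and at rho = 0.1 the power gap is only about 1.5 points. The period and interaction terms, with the interim estimate of within-patient variability, suggest that the authors had the pairing in mind and worded a synopsis loosely.

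Much of this stands. There is no inflation of false positives at positive rho, the size of the loss depends on quantities that the documents do not give, and the difference in degrees of freedom is minor here (critical values of about 1.99 and 2.03). The period bias needs both a real period effect and unequal completion by sequence. The documents do not show either, although the assumed 20% drop-off makes unequal completion possible.

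The reply does not rescue the stated method. A two-sample t test is valid in a 2x2 crossover when it compares within-patient period differences between the two *sequence* groups, but the plan names treatments as the groups and recovery time as the variable. The comfort about power also depends on reading A. Under reading B, the one that makes 35 a crossover sample size at any rho, the stated test falls well short of 80%.

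**Conclusion.** The concern holds. The primary test as written does not match the declared design, and its p value and interval are wrong whenever a patient's two recovery times are correlated.

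For rho between 0.3 and 0.7 and equal SDs, the standard error is 1.20 to 1.83 times too large and the true level is about 2% down to 0.1%. The cost in power at 36 completers is about 7 to 10 percentage points if 2.4 minutes is a total SD. If it is a within-patient SD, power drops to between 67% and 23%. The direction is conservative for positive rho, and the two analyses agree at rho = 0. The values of rho, the equal SDs and the meaning of 2.4 are assumptions. The mismatch between test and design does not depend on them.

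**What to change.** Replace the sentence naming the two-sample t test with a crossover analysis: a linear mixed model for time to T1 90% of baseline, with treatment, period and sequence as fixed effects and a random patient effect. Report the treatment coefficient with its 95% confidence interval as the primary result. For completers, a two-sample t test on the within-patient period difference between the two sequence groups is equivalent. The mixed model has the advantage that it also uses patients with only one period, in line with the stated intent-to-treat principle.

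In the sample-size paragraph, state whether 2.4 minutes is a total or a within-patient SD and, if total, which rho is assumed, so that the calculation matches the analysis.

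The cost is a sentence or two of wording, with no extra data, patients or visits. The change should be made before treatment codes are broken for the analysis.
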